7. STATISTICAL METHODS AND DETERMINATION OF SAMPLE SIZE

7.1 STATISTICAL DESIGN – MODEL

The primary objective of the study is to investigate safety and tolerability of three consecutive administrations, 12 h apart, at three different dose-levels (100, 400 and 1200 µg) of BI 443651 administered via oral inhalation in male and female mild asthmatic subjects after a bolus MCh challenge.

For the main part, the primary endpoint absolute change in maximum reduction of FEV₁ and the secondary endpoint relative change in AUC_{0-tz} as described in [Section 5.1](#) will be analysed using a mixed effects model on the original and logarithmic-scale, respectively, taking the crossover design of the trial into account. The models will include treatment and period as fixed effects, subject as a random effect and period baseline as well as subject baseline as covariates. The subject baseline will be obtained by calculating the mean of period baselines for each subject. Active doses will be compared to placebo for both endpoints. For investigation of the secondary endpoint time to recovery to within 95% of post-diluent value a Cox proportional hazards model will be used to estimate the hazard ratio of BI 443651 vs. Placebo.

For the pilot part, the primary and secondary endpoints as described in [Section 5.1](#) will be analysed using descriptive statistics. No inferential statistics are planned for this part of the trial.

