7.2 NULL AND ALTERNATIVE HYPOTHESES

Safety and tolerability of 3 different dose strengths of BI 443651 are to be determined on the basis of the investigated parameters in comparison to placebo. It is not planned to test any statistical hypotheses with regard to these variables in a confirmatory sense. Instead, they will be described in their entirety and evaluated by descriptive statistical methods.

Confidence intervals will be computed and will have to be interpreted in the perspective of the exploratory character of the study, i.e. confidence intervals are considered as interval estimates for effects.

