The secondary endpoint time to recovery of FEV₁ within 95% of post-diluent value (see [Section 5.1.2](#)) is defined as the time from maximum reduction to last time before recovery to within 95% of pre-MCh challenge during each challenge. The time obtained from the treatment challenge represents the endpoint, while the time obtained from the baseline challenge will be used for the baseline correction in the analysis.

This secondary endpoint will be investigated using descriptive statistics for both trial parts separately and combined, if applicable.

Kaplan-Meier (KM) curves will be plotted for the recovery of FEV₁ within 95% of post-diluent value by treatment irrespective of the period it is administered in, for both trial parts separately as well as combined, if applicable.

For part II of the trial, this endpoint will be analysed using a Cox proportional hazards model as given below based on the MCS. The model includes the treatment effect and an effect for subject baseline. Thereby, the subject baseline is calculated as median of all period baselines per subject. Breslow's method for handling ties will be used.

The hazard function for the ith subject is assumed to be

$$\lambda_i(t) = \lambda_0(t) \cdot \exp\{\beta_1 X_{1i} + \beta_2 X_{2i} + \beta_3 X_{3i}\},$$

where i = 1, ..., N,

$\lambda_0(t)$ is the unspecified, non-negative, baseline hazard function

- $\beta_{1,2,3}$ are the unknown regression coefficients
- X_{1i} represents the treatment group
- X_{2i} represents the subject baseline (median of period baselines)
- X_{3i} represents the period

Proprietary confidential information © 2017 Boehringer Ingelheim International GmbH or one or more of its affiliated companies

For treatment comparisons the hazard ratios of BI 443651 vs. Placebo and asymptotic 95% Wald confidence intervals will be estimated. A hazard ratio of greater than one means that BI 443651 is not inferior to placebo.

Further details will be provided in the TSAP.

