7.7 DETERMINATION OF SAMPLE SIZE

For the pilot part, it is planned to include 4 otherwise healthy asthma subjects. The planned sample size is not based on a power calculation. This sample size is considered as sufficient for the exploratory evaluation of safety after multiple doses in this study population.

For the main part, it is planned to include a total of 32 (8 per sequence) completed otherwise healthy asthma subjects (non-completed subjects will be replaced, see Section 3.3.5) to achieve the aims of this exploratory trial with the following assumptions:

- The primary endpoint is normally distributed
- Two-sided significance level $\alpha = 10\%$
- Considered relevant change: -0.2 L
- The treatment difference between the means of BI 443651 and placebo is expected to be -0.06 L [data on file]
- The within-subject standard deviation (SD) for the difference is expected to be 0.24 L [data on file]

Assuming a within-subject SD of 0.24 L for BI 443651 and given the chosen sample size of N=32 subjects, the precision of the two-sided 90% confidence interval of the difference will be approximately 0.112 (upper confidence limit (UL) – point estimate of the difference (Diff)); for a greater within-subject SD of 0.3, the precision would still be approximately 0.14.

Increasing the sample size by 4 (N=36) results in a precision of approximately 0.105 and 0.131, respectively. [Table 7.7: 1](#) provides an overview of the 90% confidence intervals that are expected with 95% tolerance probability, for possible scenarios of the SDs and intra-subject differences (active drug – placebo).

Proprietary confidential information © 2017 Boehringer Ingelheim International GmbH or one or more of its affiliated companies

Table 7.7: 1 Precision that can be expected with 95% tolerance probability and illustrative two-sided 90% confidence intervals around the treatment differences for different SDs and varying sample sizes in a 4x4x4 crossover

N	SD within	Precision (UL-Diff)	Diff (active – placebo)				
			-0.1	-0.05	0	0.05	0.1
32	0.24	0.112	(-0.21, 0.01)	(-0.16, 0.06)	(-0.11, 0.11)	(-0.06, 0.16)	(-0.01, 0.21)
32	0.3	0.14	(-0.24, 0.04)	(-0.19, 0.09)	(-0.14, 0.14)	(-0.09, 0.19)	(-0.04, 0.24)
36	0.24	0.105	(-0.20, 0.00)	(-0.15, 0.05)	(-0.10, 0.10)	(-0.05, 0.05)	(-0.00, 0.20)
36	0.3	0.131	(-0.23, 0.03)	(-0.18, 0.08)	(-0.13, 0.13)	(-0.08, 0.18)	(-0.03, 0.23)

The calculation was performed as described by Julius [R11-5230] using R Version 3.2.2.

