7.5 SECONDARY ENDPOINTS

The secondary endpoints will be analyzed based on the MCS.

Relative change from baseline in FEV₁ AUC_{0-tz} following bolus MCh challenge:

CTP: *The secondary endpoint relative change from baseline in FEV₁ AUC_{0-tz} (see Section 5.1.2 of the CTP) is defined as the ratio of FEV₁ AUC_{0-tz} obtained during the treatment challenge and during the baseline challenge. During each challenge, the area above the curve of the absolute change in FEV₁ from post-diluent value will be calculated from time 0*

to t_z using the trapezoidal rule (refer to 001-MCG-163). The time t_z refers to the last time point before recovery of FEV_1 to within 95% of post-diluent value.

Note that in case a subject's FEV_1 does not recover to within 95% of post-diluent value the time t_z refers to the last timepoint at which FEV_1 was measured for that subject in that period. Furthermore, if a subjects FEV_1 does not decrease below 95% of post-diluent value the AUC will not be defined and hence not be calculated.

Descriptive statistics and boxplots of the secondary endpoint by treatment (and by trial part) will be provided.

As main analysis, the following model will be applied to the main part of the trial (part II). The statistical model used for this secondary endpoints is comparable to the one specified for the primary endpoint, despite the fact that it is evaluated on the logarithmic scale.

Statistical model

CTP: [...] this secondary endpoint will be analysed using a mixed effects model on the logarithmic scale based on the MCS:

$$y_{imj} = \mu + \pi_m + \tau_j + \gamma b_{im} + \gamma' b'_i + s_i + e_{imj},$$

where $i = \text{subject } 1, \dots, N$, $m = \text{period } 1, \dots, 4$, $j = \text{treatment } 1, \dots, 4$

y_{imj}	Logarithm of CFB in FEV_1 AUC_{0-t_z} consideration for the i^{th} subject and the m^{th} period, receiving randomised treatment j
μ	overall intercept,
π_m	m^{th} period effect,
τ_j	j^{th} treatment effect,
b_{im}	Logarithm of baseline value for subject i in period m (period baseline),
γ	associated covariate effect of period baseline,
b'_i	Logarithm of the subject baseline value (mean of period baselines) for subject i ,
γ'	associated covariate effect of subject baseline,
s_i	the random effect of subject i ,
e_{imj}	the random error associated with subject i who received treatment j in period m .

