9.2.1 Details for primary analyses

The following SAS code can be used to fit the model for the primary endpoint:

```
PROC MIXED data=indata METHOD=reml ORDER=formatted;
  CLASS SUBJID ATRTSL APERIOD;
  MODEL CHG = ATRTSL APERIOD BASE baseavg / SOLUTION DDFM = KR
    OUTP=pred;
  RANDOM INTERCEPT / SUBJECT = SUBJID TYPE=VC;
  LSMEANS ATRTSL / PDIFF=control('Placebo') CL ALPHA=0.1;
RUN ;
```

The following SAS code can be used to fit the model for the secondary endpoint 'FEV₁ AUC0-tz':

```
PROC MIXED data= indata METHOD=reml ORDER=formatted ;
  CLASS SUBJID ATRTSL APERIOD;
  MODEL LNRATIO = ATRTSL APERIOD lnbase lnbaseavg / SOLUTION DDFM
    = KR OUTP=pred;
  RANDOM INTERCEPT / SUBJECT = SUBJID TYPE=VC;
  LSMEANS ATRTSL / PDIFF=control('Placebo') CL ALPHA=0.1;
RUN ;
```

The following SAS code can be used to fit the model for the secondary endpoint 'Time to recovery':

```
PROC PHREG DATA= adtte;
  CLASS ATRTSL (REF='Placebo') APERIOD;
  MODEL aval*cnsr(1) = ATRTSL APERIOD BASEAVG / TIES=BRESLOW;
  HAZARDRATIO ATRTSL / DIFF=REF CL=WALD ALPHA=0.05;
  ODS OUTPUT HAZARDRATIOS=hazard;
RUN;
```

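### A hazard ratio above 1 for time to recovery is equated with non-inferiority, with no margin on the hazard-ratio scale and no use of the planned 95% CI

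*Protocol*

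**What the plan says.** Protocol Section 7.1 gives the purpose of the Cox analysis: "a Cox proportional hazards model will be used to estimate the hazard ratio of BI 443651 vs. Placebo". Section 7.3.2 specifies hazard ratios with asymptotic 95% Wald intervals and then adds: "A hazard ratio of greater than one means that BI 443651 is not inferior to placebo". SAP Section 7.5 repeats that sentence unchanged and attaches neither a margin nor a confidence limit to it.

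The SAP code (Section 9.2.1) fits "MODEL aval*cnsr(1) = ATRTSL APERIOD BASEAVG / TIES=BRESLOW" with placebo as the reference treatment, and requests the interval with "HAZARDRATIO ATRTSL / DIFF=REF CL=WALD ALPHA=0.05". It contains no comparison with a margin.

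On inference in general, protocol Section 7.2 says "It is not planned to test any statistical hypotheses with regard to these variables in a confirmatory sense" and adds that "confidence intervals are considered as interval estimates for effects". The only relevance threshold in either document is in protocol Section 7.7, "Considered relevant change: -0.2 L". It is in litres and belongs to the primary endpoint.

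**The concern.** Non-inferiority means that a loss larger than a stated amount has been excluded with stated confidence. A point estimate on the favourable side of 1 does not do that. Here the estimate alone carries the conclusion, although the interval that could qualify it is planned in the sentence just before. The sentence also runs against Section 7.2, which keeps the analysis to estimation.

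A report that followed the plan literally could describe a dose as not inferior on recovery from bronchoconstriction while its interval included clearly slower recovery. Protocol Section 2.1 presents the trial as a check for harmful effects on lung function before larger studies, so unsupported reassurance is the more serious direction of error. The reach is limited: this is a secondary endpoint, and no stopping rule, progression rule or sample size uses the hazard ratio.

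**Working it through.** **Figures in the plan.** Neither document gives an expected number of recoveries, a power or a margin for the hazard ratio, so there is no figure for this endpoint to reproduce. The one precision figure, 0.112 L for the primary endpoint, does reproduce: t(0.95; 90) × 0.24 × √(2/32) = 0.0997, and multiplying by √(χ²(0.95; 90)/90) gives 0.1118. It has no bearing on the hazard ratio.

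**Direction.** The event is recovery and the reference is placebo. A ratio above 1 means faster recovery on BI 443651, so the sentence has the direction right.

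**Inputs.**
- Part 2 plans 32 completers, each receiving all four treatments (protocol Section 7.7). That gives about 32 recoveries per treatment at most, apart from any contribution by replaced subjects.
- The count could be lower. The code allows censored times, the methacholine set leaves out measurements affected by rescue use within 3 hours, and SAP Section 7.5 caters for a subject whose FEV₁ "does not recover to within 95% of post-diluent value" (there, to define the AUC endpoint). No rates are given, so d = 32, 24 and 16 recoveries per treatment is an assumed range.

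**Formulas** (covariates and ties ignored):
- SE of the log hazard ratio ≈ √(1/d + 1/d)
- 95% CI at an estimate of 1 = exp(±1.96 × SE)
- P(estimate > 1) = Φ(ln(true HR)/SE)

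**Results with independent arms:**

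| d per treatment | SE | 95% CI at estimate 1 | P(estimate > 1), true HR 0.9 | P(estimate > 1), true HR 0.8 |
|---|---|---|---|---|
| 32 | 0.250 | 0.61 to 1.63 | 33.7% | 18.6% |
| 24 | 0.289 | 0.57 to 1.76 | 35.8% | 22.0% |
| 16 | 0.354 | 0.50 to 2.00 | 38.3% | 26.4% |

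Example for d = 32: ln(0.8)/0.250 = −0.223/0.250 = −0.893, and Φ(−0.893) = 0.186.

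**Within-subject correlation.** In a crossover the two times being compared come from the same subject. With an assumed correlation r and d = 32, the sampling SE is √((2/32)(1 − r)):

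| r | SE | P(estimate > 1), true HR 0.9 | P(estimate > 1), true HR 0.8 |
|---|---|---|---|
| 0.3 | 0.209 | 30.7% | 14.3% |
| 0.5 | 0.177 | 27.6% | 10.3% |
| 0.7 | 0.137 | 22.1% | 5.2% |

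The SAP code has no subject term, so the interval it prints corresponds to the independent-arms SE.

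**What the sentence guarantees.** An estimate above 1 ensures only that the lower 95% limit exceeds exp(−1.96 × SE): 0.61, 0.57 or 0.50 for the three counts. Used as a criterion, it would be an unstated margin that loosens as fewer recoveries are observed.

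**Comparison with a criterion based on the interval.** At SE 0.250, a lower limit above 0.8 would need an observed ratio above 0.8 × 1.63 = 1.31, and a lower limit above 0.7 would need 0.7 × 1.63 = 1.14. The values 0.8 and 0.7 are illustrations only; the documents give no margin.

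**The case against.** The strongest defence is that the sentence only explains direction. It says what a ratio above 1 means, not that a conclusion will be declared, and as a statement about the true ratio it is correct. Section 7.2 already rules out confirmatory testing, and the interval will be reported beside the estimate, so a reader would see the uncertainty. On this view the percentages above describe any estimator and would be the same after rewording.

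Part of this stands. Direction may well have been the intent. Section 7.1 is compatible with a note on direction and adds little to the conflict. The non-recovery wording in the SAP serves the AUC endpoint, the censoring indicator implies no particular rate, and 16 recoveries is only an assumed low case. The percentages are chances of an estimate in the wrong direction. They are not false non-inferiority rates, which cannot be computed without a margin.

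The defence does not remove the point. The words state a non-inferiority conclusion, in two documents, next to an interval they do not use. Section 7.2 contradicts that conclusion and so does not repair it. If direction was meant, saying so loses nothing.

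**Conclusion.** The concern holds. As written, the plan equates a point estimate above 1 with non-inferiority, without a hazard-ratio margin and without the interval it has just specified. With at most about 32 recoveries per treatment, an estimate just above 1 would typically come with an interval reaching down to about 0.6, which does not exclude clearly slower recovery. The size rests on assumed recovery counts, a simple SE approximation and, for the lower probabilities, assumed correlations. The conclusion that the sentence is unsupported rests on none of these. It should be fixed, but the consequence is limited to how one secondary safety endpoint is reported.

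**What to change.** Replace the sentence in protocol Section 7.3.2 and SAP Section 7.5 with:

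> A hazard ratio above 1 indicates faster recovery, and a ratio below 1 slower recovery, on BI 443651 than on placebo. The ratio and its 95% CI are reported as interval estimates, and no non-inferiority conclusion is drawn.

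The cost is one sentence per document. Endpoint, model, code and sample size are unchanged. Protocol Section 8.1 makes amendments subject to approval. If that is disproportionate here, the SAP alone can carry the wording, recorded in its Section 4 as a change from the protocol.

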7.3.5 Safety analyses

Safety will be assessed for the further safety parameters of interest listed in [Section 5.1.3](#) based on the TS. Safety analyses will be descriptive in nature and will be based on BI standards.

Treatments will be compared in a descriptive way. The active treatment groups will be compared to the placebo group in a descriptive way. Tabulations of frequencies/proportions will be used for the evaluation of categorical (qualitative) data, and tabulations of descriptive statistics will be used to analyse continuous (quantitative) data.

The analyses will be done by ‘treatment at onset’.

Measurements (such as ECG, vital signs, or laboratory parameters) or Aes will be assigned to treatments (see [Section 4.1](#)) based on the actual treatment at the planned time of the measurement or on the recorded time of AE onset (concept of treatment emergent Aes).

Therefore, measurements planned or Aes recorded prior to first intake of trial medication will be assigned to ‘screening’, those between first trial medication intake until next intake or end of REP will be assigned to the preceding treatment, and all Aes occurring between the end of REP and next treatment intake or trial termination date respectively will be assigned to ‘follow-up’. In case of two or more treatments, the follow-up will be summarized according to the previous treatment. These assignments including the corresponding time intervals will be defined in detail in the TSAP. Please note that Aes occurring after the last per protocol contact but entered before database lock will be reported to drug safety only and will not be captured in the trial database.

Additionally, further treatment intervals (analysing treatments) may be defined in order to provide summary statistics for time intervals, such as combined treatments, on-treatment totals or periods without treatment effects (such as screening and follow-up intervals).

Adverse events will be coded using the Medical Dictionary for Regulatory Activities (MedDRA). Frequency, intensity and causal relationship of Aes will be tabulated by treatment, primary system organ class and preferred term. SAEs, AESIs ([see Section 5.3.6](#)) and other significant Aes (according to ICH E3) will be listed separately.

Laboratory data will be compared to their reference ranges. Values outside the reference range will be flagged. Additionally, differences from baseline will be evaluated.

Vital signs, physical examinations, or other safety-relevant data observed at screening, baseline, during the course of the trial and at the end-of-trial evaluation will be assessed with regard to possible changes compared to findings before start of treatment.

7.4 INTERIM ANALYSES

No inferential statistical interim analysis is planned. However, after part 1 the investigator (or his deputy) is allowed to postpone progression to part 2 until a preliminary safety review (see [Section 3.1](#)) of the data already obtained has been performed. For handling of treatment blinding refer to [Section 4.1.5](#).

7.5 HANDLING OF MISSING DATA

7.5.1 Safety

For evaluation of primary and secondary endpoints a measurement obtained at baseline and on-treatment per period is required. Further details will be provided in the TSAP.

Handling of drop-outs is described in [Section 3.3.5](#).

With respect to further safety evaluations (refer to [Section 7.3.4](#)), it is not planned to impute missing values.

7.6 RANDOMISATION

For each trial part, subjects will be randomised to one of four treatment sequences (see [Section 3.1](#)) in a 1:1:1:1 ratio. The block size will be documented in the CTR.

The sponsor will arrange for the randomisation as well as packaging and labelling of trial medication. The randomisation list will be generated using a validated system, which involves a pseudo-random number generator and a supplied seed number so that the resulting allocation is both reproducible and non-predictable.

The randomisation list will contain additional blocks to allow for subject replacement (refer to [Section 3.3.5](#)).

7.7 DETERMINATION OF SAMPLE SIZE

For the pilot part, it is planned to include 4 otherwise healthy asthma subjects. The planned sample size is not based on a power calculation. This sample size is considered as sufficient for the exploratory evaluation of safety after multiple doses in this study population.

For the main part, it is planned to include a total of 32 (8 per sequence) completed otherwise healthy asthma subjects (non-completed subjects will be replaced, see Section 3.3.5) to achieve the aims of this exploratory trial with the following assumptions:

- The primary endpoint is normally distributed
- Two-sided significance level $\alpha = 10\%$
- Considered relevant change: -0.2 L
- The treatment difference between the means of BI 443651 and placebo is expected to be -0.06 L [data on file]
- The within-subject standard deviation (SD) for the difference is expected to be 0.24 L [data on file]

Assuming a within-subject SD of 0.24 L for BI 443651 and given the chosen sample size of N=32 subjects, the precision of the two-sided 90% confidence interval of the difference will be approximately 0.112 (upper confidence limit (UL) – point estimate of the difference (Diff)); for a greater within-subject SD of 0.3, the precision would still be approximately 0.14.

Increasing the sample size by 4 (N=36) results in a precision of approximately 0.105 and 0.131, respectively. [Table 7.7: 1](#) provides an overview of the 90% confidence intervals that are expected with 95% tolerance probability, for possible scenarios of the SDs and intra-subject differences (active drug – placebo).

Proprietary confidential information © 2017 Boehringer Ingelheim International GmbH or one or more of its affiliated companies

Table 7.7: 1 Precision that can be expected with 95% tolerance probability and illustrative two-sided 90% confidence intervals around the treatment differences for different SDs and varying sample sizes in a 4x4x4 crossover

N	SD within	Precision (UL-Diff)	Diff (active – placebo)				
			-0.1	-0.05	0	0.05	0.1
32	0.24	0.112	(-0.21, 0.01)	(-0.16, 0.06)	(-0.11, 0.11)	(-0.06, 0.16)	(-0.01, 0.21)
32	0.3	0.14	(-0.24, 0.04)	(-0.19, 0.09)	(-0.14, 0.14)	(-0.09, 0.19)	(-0.04, 0.24)
36	0.24	0.105	(-0.20, 0.00)	(-0.15, 0.05)	(-0.10, 0.10)	(-0.05, 0.05)	(-0.00, 0.20)
36	0.3	0.131	(-0.23, 0.03)	(-0.18, 0.08)	(-0.13, 0.13)	(-0.08, 0.18)	(-0.03, 0.23)

The calculation was performed as described by Julius [R11-5230] using R Version 3.2.2.

